### **10. SAMPLE SIZE DETERMINATION AND DATA ANALYSIS**

### 10.1. Sample Size Determination

Power analyses were performed for the three primary objectives, using a power level of 0.80 and an alpha

Protocol #: IU IRB# 1810997768 Date: 31AUG21 Page 13 of 17

level of 0.05. Based on the literature the incidence of hypoxemia (ie: oxygen saturation < 90% for > 15 seconds) in using supplemental oxygen with nasal cannula is as high 43%. (Patel et. al.) Thus we expect the complication rate of hypoxemia in the SuperNO2VA EtM group to be 13%, we need 62 patients per group (124 patients in total). This sample size will allow us to detect this expected difference with 80% power at 0.05 two sided level of significance. To adjust for 10% missing rate, we need approximately 124 patients in total.

### 10.2. Randomization

A random number generator program will be used to assign sequential qualified study cases to control group (N = 62) or SuperNO2VATMEtCO2 group (N = 62) before collection of additional demographic information and before anesthetic and surgical care. After study group assignment, baseline data will be collected, including age, gender, height, weight, and BMI.

#### **10.3.** Planned Statistical Analysis

Although randomization into treatment groups should minimize differences between the groups, basic bivariate analyses will be performed to determine if there are any clinical or demographic differences, using the data collected in table 1. Logistic regression models will be performed to determine if there are significant differences between the groups for both incidence and severity. Student's t-tests will be performed to determine if there is a significant difference between groups for duration, with Wilcoxon non-parametric tests being performed if the data are non-linear. If significant differences in clinical or demographics characteristics were found, multivariable models will be performed to adjust for these possible confounding variables using logistic regression and ANCOVA models (with GEE models being used to model non-linear data with the appropriate exponential family distribution). All analytic assumptions will be verified and all analyses performed with SAS v9.4, SAS Institute, Cary, NC), analyzing the data as both per-protocol and intention-to-treat.

A Data Safety and Monitoring Board (DSMB) will be convened once half the necessary study population has been enrolled, to discuss the current status of primary endpoints and adverse events, all of which will be tabulated throughout the study. If effect sizes are larger than originally planned and there is a statistically significant decrease in the primary event at this halfway mark, the study will end at this time.

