# **Endpoints of Interest**

- 1. Compare the amount of propofol administered during induction and total dose administered for procedure
- 2. Compare Modified Observer's Assessment of Alertness/Sedation Scale (MOAAS) scores immediately prior to endoscopic intubation and during the procedure

Protocol #: IU IRB# 1810997768 Date: 31AUG21 Page 5 of 17

- 3. Compare the length of time from induction to endoscopic insertion
- 4. Compare the incidence and duration of procedural interruptions (ie: number of times and length of time the endoscope is removed from the patient)
- 5. Compare the incidence, duration, and reason for airway maneuvers
- 6. Compare the length of time for the procedure (ie: length of time from procedure start to procedure end)
- 7. Compare recovery times
- 8. Compare patient satisfaction scores (visual analog scale (VAS)) immediately after procedure
- 9. Compare patient satisfaction scores 48 hours later
- 10. Compare patient tolerance to SuperNO2VA EtCO2 compared to control (ie: nasal cannula at 10LPM)
- 11. Compare endoscopist satisfaction scores for
- 12. Compare anesthesiologists satisfaction scores
- 13. Compare the incidence of cardiac complications

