### 5.4 Crossover to Other Group After Randomization

Patients in either Group A or Group B will be eligible for crossover to the other group at the discretion of the anesthesiologist in order to safely complete the procedure and minimize the likelihood of future adverse events.

Group A (Standard care with a nasal cannula) to Group B (SuperNO2VA™EtCO2) group will occur when during the procedure either: 1) twoor more simultaneous or non-synchronous adverse events related to changes in SBP, SpO2 or HR that do not respond to typical maneuvers to reverse these or; 2) any of the following two occur: a) any change in heart rhythm other than sinus bradycardia or sinus tachycardia or; b) ST changes appear on EKG occur.

Group B to Group A: If any of the following occur: 1) patient refusal to wear the mask once placed due to claustrophobia, poor fit or discomfort or any other reason; 2) two or more simultaneous or non-synchronous adverse events related to changes in SBP, Sp02 or HR that do not respond to typical maneuvers to reverse these or; 3) any of the following two occur: a) any change in heart rhythm other than sinus bradycardia or sinus tachycardia or; b) ST changes appear on EKG occur.

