### **Adverse Events**

For study conduct purposes, adverse events will be categorized at the investigative site into two groups: Serious Adverse Events, and Non-Serious Adverse Events. The Investigator as either related to the device or its deployment, or not related to the device or its deployment will assess the causal relationship of each adverse event. Each Adverse Event assessed as being related to the device or its deployment will also be assessed by the Investigator as being anticipated or unanticipated.

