### 7.3. Responsibilities for Reporting Serious Adverse Events

All adverse events, whether observed by the Investigator, elicited from or volunteered by the subject, should be documented. Each adverse event will include a brief description of the experience, the date of onset, the date of resolution, the duration and type of experience, the severity, the relationship to investigational product (i.e., drug or device), contributing factors, and any action taken with respect to the study drug/device.

Investigators and research coordinators will be instructed that all AE and corresponding relevant information should be recorded on the Adverse Event Form. In addition, the clinical site will be responsible for notifying Sponsor within 24 hours of any UADE. All relevant information regarding an UADE should be recorded on the Adverse Event Form and reported to Sponsor via Fax within 24 hours of the event. In addition to the event form, copies of adverse device effect related source documents should be forwarded to the Sponsor.

The Principal Investigator is responsible for reporting AEs to the IRB of record in accordance with IRB procedures. The Sponsor is responsible for informing the appropriate regulatory authorities and other Investigators of any UADEs that have occurred.

The Principal Investigator will record all serious adverse experiences that occur during the study period in the appropriate source documents and/or AE log as applicable.

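### Patients may switch device in either direction, but no safety table by device exposure is planned and the listed fields cannot place events before or after a switch

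*Protocol*

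**What the plan says.** **Switching.** Protocol 5.4 states: "Patients in either Group A or Group B will be eligible for crossover to the other group at the discretion of the anesthesiologist". Cannula patients (Group A) may move to the mask after two or more blood pressure, saturation or heart rate events that do not resolve with the usual measures, or after a rhythm or ST change. Mask patients (Group B) may move to the cannula on the same grounds, and also after "patient refusal to wear the mask once placed due to claustrophobia, poor fit or discomfort or any other reason".

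**Analysis.** Protocol 10.3, repeated in SAP 1.3, closes its paragraph on statistical models with "analyzing the data as both per-protocol and intention-to-treat". Neither document defines per-protocol, names a safety or as-treated set, or says where an event after a switch is counted. The next paragraph has a monitoring board meet at the halfway mark "to discuss the current status of primary endpoints and adverse events, all of which will be tabulated throughout the study". No grouping or denominator is given for that tabulation.

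**Safety data.** Under Adverse Events in 7.1, the investigator judges whether each event is "related to the device or its deployment". "Each Adverse Event assessed as being related to the device or its deployment" is then also classed as anticipated or not. Section 7.3 asks for "the date of onset, the date of resolution, the duration and type of experience", along with contributing factors and any action taken with the study device. The measurements listed in 5.2 do not include a device change or its time. Endpoint 13 reads "Compare the incidence of cardiac complications".

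**The concern.** One patient can wear both devices in a single session, so assigned group and device worn can differ when an event occurs. Both named analysis bases start from the assigned group. Neither yields the number of patients ever exposed to the mask, which is the natural denominator for harms such as the eye injury, pressure ulcer and allergic reaction listed in 8.1.

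Two things are at stake. First, the halfway review and the final safety review (Protocol section 12, Data Safety Monitoring) could receive adverse event counts with no stated exposure basis, in a trial of a device. Second, a table can be added late, but timing that was never collected may not be recoverable. A calendar date cannot order two events within one endoscopy.

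**Working it through.** The plan states no figure on this point, so there is none to reproduce. The check traces where each kind of event falls, then does the denominator arithmetic.

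**1. Where an event is counted**

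| Event | Intention-to-treat | Per-protocol (undefined) |
|---|---|---|
| Mask-related, after a cannula-to-mask switch | Cannula | Dropped if switched patients are excluded; cannula if a permitted switch counts as adherent |
| Cannula-period, after a mask-to-cannula switch | Mask | Dropped, or mask, on the same two readings |
| The event that triggers a switch | Assigned device, which is correct | Dropped, or assigned device |

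In the first two rows neither basis puts the event with the device concerned.

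**2. Mask-exposed denominator**

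Inputs: 62 per arm (Protocol 10.2). All 62 Group B patients are taken as exposed, because the refusal ground in 5.4 applies after the mask has been placed. The cannula-to-mask rate c is not in the documents; 5% to 20% is assumed.

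Switched patients = 62 × c, rounded. Ever on the mask = 62 + switched. Share outside the Group B column = switched / (62 + switched).

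| Assumed c | Switched | Ever on mask | Share outside Group B column |
|---|---|---|---|
| 5% | 3.1, taken as 3 | 65 | 3/65 = 4.6% |
| 10% | 6.2, taken as 6 | 68 | 6/68 = 8.8% |
| 20% | 12.4, taken as 12 | 74 | 12/74 = 16.2% |

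**3. Direction of the distortion (invented counts, for illustration)**

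- Two mask injuries in Group B and one in a switched Group A patient: intention-to-treat shows 2/62 = 3.2% against 1/62 = 1.6%. Per mask-exposed patient the rate is 3/65 = 4.6% to 3/74 = 4.1%. The mask column is too low.
- Two in Group B and none in switched patients: intention-to-treat shows 2/62 = 3.2%. Per mask-exposed patient it is 2/65 = 3.1% to 2/74 = 2.7%. The mask column is too high.
- Two events in Group B, one of them unrelated to the mask and arising on the cannula after a switch: intention-to-treat still shows 2/62 = 3.2%, while the mask accounts for 1/65 = 1.5% to 1/74 = 1.4%. The mask column is again too high.

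The direction therefore depends on who switches and when events occur.

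**4. Cardiac complications**

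Section 5.3 defines these by blood pressure or heart rate changes above 25%, arrhythmia, or ST change. The endpoint is an incidence, so a patient counts once. Someone who switches because of a rhythm or ST change already has the outcome, on the assigned device, and later events do not alter the count. Misplacement needs a switch without the definition having been met, for example a Group A patient switched on saturation events alone or a Group B patient who refuses the mask, followed by a first cardiac event on the other device.

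**The case against.** The strongest reply is that the plan already handles attribution case by case. The mask is the investigational device, every event is judged for relation to it, and 7.3 adds contributing factors and action taken with the device. Unanticipated device effects go to the sponsor within 24 hours, and two gastroenterologists outside the study review each serious event within 24 hours. A corneal abrasion in a switched cannula patient would be recorded as device-related whatever analysis set is used. Few such events are likely in 124 patients, and the Group A switching grounds are narrow. This stands for individual cases. It does not supply a rate or a denominator, and it does not supply the time of a switch. The intraoperative record or the entry on action taken may show that a device was changed, but nothing listed requires when.

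A second reply is that the named analysis sets close a paragraph about models for incidence, severity and duration, while adverse events come in a separate paragraph with no layout. That also stands. A reader might infer that every planned safety table has the wrong denominator; the documents support only that none is specified.

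Third, recording only the device worn at onset would misplace delayed harms. A pressure mark or allergic reaction may appear after the mask is off. This is correct, and the fix allows for it.

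**Conclusion.** The point holds as a gap in safety reporting and data capture. Crossover is planned in both directions, no analysis by device exposure is named, and the listed fields do not allow events in one procedure to be ordered around a switch. At an assumed 5% to 20% switching from cannula to mask, about 5% to 16% of mask-exposed patients would fall outside the Group B column. That range rests wholly on the assumed rate and on all 62 Group B patients having had the mask placed.

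Three stronger readings are tempting, and the documents do not support them. A reader might infer that the mask's event rate is understated; the illustrations show that it can go either way. A reader might infer that per-protocol analysis certainly drops switched patients; the term is undefined, and a switch that 5.4 permits could count as adherent. A reader might infer that cardiac complications are generally misattributed because rhythm and ST changes both define the outcome and trigger the switch; a trigger comes before the switch and is correctly counted under the assigned device, so only patients who switch without already meeting the definition are affected.

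The primary efficacy comparison is not touched by this point. The change is still worth making while data can be collected.

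**What to change.** - **Data capture.** Add to the case report form the clock time of any device switch. Add to the Adverse Event Form the clock time of onset and the device or devices worn up to onset.
- **Analysis.** In Protocol 10.3 and SAP 1.3, keep the randomised comparison and add one descriptive safety table by device exposure, covering adverse events, adverse device effects and cardiac complications. The denominator for each device is all patients ever exposed to it, so switched patients enter both. Split events into before and after the switch. Count events judged related to the mask under the mask even if they appear after its removal. Do not move whole patients between columns, because events that trigger a switch belong to the assigned device.
- **Use.** Give this table to the halfway and final safety reviews, with the number of switches in each direction.

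The cost is a few form fields and one table. The downside is that the by-exposure table is not a randomised comparison: switched patients are selected by their course during the procedure. It describes device harm and should be labelled that way. The switching rule itself need not change for this.

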MOAA/S is <4. The measurements that will be made are the following: the incidence, severity, and time of oxygen desaturation, number of airway maneuvers performed, duration of airway maneuvers, reason for performing the airway maneuver, the onset time of administration of sedation, the duration of the procedure, the total dosage of the medication, vital signs - blood pressure, heart rate, and oxygen saturation, the time to full recovery, and patient cooperation. Nursing or the research assistant will document their patient's depth of sedation, cooperation with procedure, and safety. Patients will recover in the endoscopy suite. The patients will have continuous monitoring of heart rate, end tidal CO2 (EtCO2), O2 saturation, and every 5-minute BP monitoring and MOAAS Score. The time to discharge will be obtained for each patient. Patients will also complete a satisfaction and pain questionnaire before they are discharged. Patients will also be asked to complete another questionnaire within 48 hours concerning their satisfaction and their subjective degree of impairment due to the sedation either with a paper form and self-addressed envelope or electronically sent via e mail. If the patients do not complete their questionnaire, someone will contact them by telephone to collect the data. A statistician using student T-test, Fishers exact test, and other statistical methods they deem appropriate will analyze the collected data.

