### **Data Safety Monitoring**

Two gastroenterologists ([name] and [name]), who are not a part of the study, will review adverse events, serious adverse and protocol deviations at the Indiana University site. These events and deviations will also be reported to the IU IRB as required. They will review all serious adverse events within 24 hours of their occurrence. Once 62 participants have been randomized, an interim analysis will be completed to review efficacy of primary endpoint, adverse events, serious adverse and protocol deviations. A final safety review will be performed once all the subjects complete the study.

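### The mandatory efficacy stop at 62 of 124 patients names no effect scale and does not divide the stated two-sided 0.05 between the interim and final looks

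*Protocol*

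**What the plan says.** Protocol 10.3, repeated word for word in SAP 1.3, sets two conditions at the halfway point: "If effect sizes are larger than originally planned and there is a statistically significant decrease in the primary event at this halfway mark". If both hold, "the study will end at this time". Protocol section 12 (Data Safety Monitoring) confirms the look and its timing: "Once 62 participants have been randomized, an interim analysis will be completed to review efficacy of primary endpoint". It adds no boundary.

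The only significance level is in the sample-size text (Protocol 10.1, SAP 1.1 and the Summary Table): "This sample size will allow us to detect this expected difference with 80% power at 0.05 two sided level of significance". It is stated for the trial as a whole and is not assigned to either look.

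For the test, 10.3 says: "Logistic regression models will be performed to determine if there are significant differences between the groups for both incidence and severity". It does not say whether the logistic p-value is Wald or likelihood-ratio. Protocol 5.2 has a general list for all data: "A statistician using student T-test, Fishers exact test, and other statistical methods they deem appropriate will analyze the collected data". Section 10.3 also calls for both per-protocol and intention-to-treat analyses without saying which one drives the stop. It speaks of primary endpoints in the plural and then of one primary event, while the primary objective covers incidence, duration and severity.

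**The concern.** A rule that ends a trial should give one answer for one interim table. This one requires the observed effect to exceed the planned effect, but the plan gives the planned effect only as two rates. The sample-size text treats the gap between them as a difference, which favours a 30-point threshold. The model named for incidence is logistic, whose natural effect measure is the odds ratio. Each reading has support in the text.

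The second condition, significance, has no interim level and no matching final level. If 0.05 is used at both looks by default, the overall error is no longer controlled by design.

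At stake are whether the trial ends with half its patients, how precise its estimate then is, and whether the stated two-sided 0.05 holds.

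**Working it through.** **Inputs.** Control rate 43%, device rate 13%, two-sided 0.05, 80% power, 62 per group (Protocol 10.1, SAP 1.1). Look at 62 randomized (section 12). Assumed: 31 per arm at the look, 62 per arm at the end, no missing data, and a Wald test counted as not significant when a cell is zero.

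**The plan's own sample size.** Pooled formula: n = [1.960·√(2·0.28·0.72) + 0.842·√(0.43·0.57 + 0.13·0.87)]² / 0.30² = (1.245 + 0.504)² / 0.09 ≈ 34 per arm. The stated 62 is not reproduced at 80% power; 62 per arm gives 96.9%. That is a separate matter and does not change this point. It does mean that a halfway point defined as "once half the necessary study population has been enrolled" could be read as 56 (half of the 112 in the Summary Table); section 12 settles on 62.

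**Planned effect on each scale.**
- Difference: 0.43 − 0.13 = 0.30.
- Risk ratio: 0.13/0.43 = 0.302.
- Odds ratio: (0.13/0.87)/(0.43/0.57) = 0.198.

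**Two interim tables (control versus device).**

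| | 9/31 vs 2/31 | 16/31 vs 6/31 |
|---|---|---|
| Difference | 7/31 = 22.6 points: continue | 10/31 = 32.3 points: stop |
| Risk ratio | 2/9 = 0.22: stop | 6/16 = 0.375: continue |
| Odds ratio | (2·22)/(9·29) = 0.17: stop | (6·15)/(16·25) = 0.225: continue |
| Wald p | 0.032 | 0.010 |
| Likelihood-ratio p | 0.016 | 0.007 |
| Fisher p | 0.043 | 0.016 |

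Wald for the first table: ln(44/261) = −1.780; SE = √(1/9 + 1/22 + 1/2 + 1/29) = 0.831; z = −2.14. Both tables are significant at 0.05 by every test, so the scale alone reverses the decision.

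**How often.** Every 31-by-31 table was weighted by its binomial probability, with a stop defined as p<0.05 for a decrease plus the effect condition. The difference and risk-ratio readings disagree in 15-17% of trials at 43% versus 13%, depending on the test. If those trials continue to 124, about 99% reject at the final 0.05 test. At an illustrative 30% versus 13% (the 30% is not in the plan), they disagree in 14-20%, and 88-91% of those reject at the end.

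**Type I error with 0.05 at both looks** (two-stage enumeration, common event rates 10-45%, rule versus no look).
- Difference scale: the look adds at most 0.35 points (logistic) or 0.42 points (Fisher, total 4.2%). At a common rate of 43%, logistic gives 6.0% versus 5.6%.
- Risk-ratio scale, likelihood-ratio test: 7.9% versus 5.9% at an illustrative common rate of 13%, and 8.6% versus 6.1% at 10%, the bottom of the range. Wald at 13%: 4.6% versus 4.0%.
- Fisher at both looks: at or below 4.2% on every scale.

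With the plan's 10% missing (28 then 56 per arm), the difference-scale addition is at most 0.6 points (logistic) or 0.7 points (Fisher, total below 4%). The risk-ratio, likelihood-ratio case at 13% is 8.0% versus 5.8%.

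**The case against.** The strongest reply is that the plan can be applied by default: two-sided 0.05 is stated for the trial, the planned effect is described as a difference, and 10.3 names logistic regression for incidence, which should govern over the general list in 5.2. On that reading the look adds less than half a point of type I error with full data, and most of the excess over 5% at a 43% rate is the logistic test's own small-sample error.

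Much of this stands. The difference reading is the likelier one, and the choice of test narrows mainly to Wald or likelihood-ratio. But the default supplies a level without defining the scale. Both example tables already use 0.05 and still reverse.

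Four stronger inferences are not supported:
- **That the plan has no significance level.** It has one; what is missing is its division between the looks.
- **That type I error rises to 8.3%,** the figure for two unadjusted two-sided looks at 0.05. The rule stops only for a decrease and also requires a large effect, so that figure does not describe it.
- **That the ambiguity often reverses the trial's conclusion.** Most trials on which the readings disagree would still reject at the end.
- **That someone will choose the scale after seeing the data.** The wording leaves room for it, but 10.3 gives the look to a DSMB and section 12 to reviewers outside the study. Nothing documents such an intention.

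**Conclusion.** The point holds and should be fixed. A mandatory stop gives opposite decisions from the same table according to a scale that the plan does not define, and the stated 0.05 is not allocated between the looks. The analysis set (which matters because Protocol 5.4 permits crossover) and the component of the primary outcome that drives the stop are also open.

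The main consequence is an early-stopping decision that cannot be reproduced, in 15-17% of trials at the planned rates for difference versus risk ratio. It affects timing and precision more than the final conclusion. The error consequence is small on the likeliest reading. The 7.9-8.6% range needs a ratio scale, a likelihood-ratio test and event rates of 10-13% together, well below the 43% planned for control. These figures assume equal arms of 31 at the look and complete data, except where 10% missing is stated.

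**What to change.** In Protocol 10.3 and SAP 1.3, with a cross-reference from section 12:

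1. Base the interim decision on incidence of desaturation, in the intention-to-treat set, with one named test: logistic (stating Wald or likelihood-ratio) or Fisher. Fisher keeps the error below 5% at all common rates of 10-45%, but at the illustrative 30% versus 13% its power without a look is 56%, against 64% (Wald) and 66% (likelihood-ratio).
2. State an interim boundary and its matching final level, for example O'Brien-Fleming: z = 2.797 (two-sided p of about 0.005) at 62 patients and z = 2.797/√2 ≈ 1.98 (p of about 0.048) at 124.
3. Delete the effect-size condition, or define its scale and keep it only in addition to the boundary.

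Cost: one paragraph, repeated in the SAP. At 43% versus 13%, power is 96.9% against 97.0% without a look (Wald), 97.2% against 97.3% (likelihood-ratio) and 95.5% against 95.6% (Fisher), a loss of about 0.1-0.2 points. At 30% versus 13%, logistic loses up to 1.8 points. Early stops at 43% versus 13% become 33% (Wald), 36% (Fisher) or 47% (likelihood-ratio), against 47-53% under the current rule across scales and tests.

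With this boundary the look adds at most 0.13 points of type I error. It does not remove the chosen test's own small-sample error: the likelihood-ratio test still gives 5.8% at a common rate of 43%.
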